14.4 Protocol Deviations and Amendments

14.4.1 Protocol Deviations

Investigators will not deviate from or alter the CTP without written agreement between the principal investigator and the sponsor and written approval by the IEC/IRB based on prior review. Exceptionally, in case of urgent clinical need (e.g., to minimize emergent risk to a subject), the principal investigator may deviate from the protocol without this written agreement. After mitigating the immediate risk, the investigator must contact the sponsor and the CRO without delay to report the incident.

In the event that an investigator does not comply with the Clinical Trial Agreement or the CTP, the sponsor will be notified of the site's noncompliance.

In the event of repeated noncompliance, as determined by the sponsor, a sponsor's monitor or company representative will attempt to secure compliance by one or more of (and not limited to) the following:

- Visiting the investigator;
- Telephoning the investigator; and/or
- Corresponding with the investigator.

Repeated noncompliance with the signed Clinical Trial Agreement, the CTP, or any other conditions of the trial may result in further escalation in accordance with the sponsor's written procedures, including securing compliance or, at its sole discretion, the sponsor may terminate the investigator's participation in the trial.

If CTP deviations occur at the investigative site, these will be detected during routine monitoring visits and reported in the visit report. In addition, a list containing all deviations reported from monitoring visits will be maintained by the CRO, analyzed for frequency and severity, and discussed with the sponsor on a regular basis. Depending on the type of deviation, corrective and preventive actions will be defined and implemented accordingly.

14.4.2 Protocol Amendments

Approved CTP amendments will be provided to investigators by the sponsor. The principal investigator is responsible for notifying the IRB/IEC of the CTP amendment (if administrative changes) or obtaining IRB/IEC's approval of the CTP amendment (if changes in subject care or safety), according to instructions provided by the sponsor.

Acknowledgement/approval by the IRB/IEC must be documented in writing prior to implementation of the CTP amendment. Copies of this documentation must also be provided to the sponsor.

14.5 Record Retention

Essential documents should be retained per applicable regulations and as instructed by the sponsor. Essential documents at the investigative site include, but are not limited to:

- Source documentation (e.g., subject files);
- Subject identification code list (i.e., provided by template to the investigator, along with the Investigator Site File, at the beginning of the investigation), which identifies the subject by number, name, and date of birth;
- A copy of the CTP and any amendments;
- A CD/DVD with eCRF data and any associated subject-related source data (or, where applicable, authorized copies of source data);
- Signed ICFs;
- Copies of site investigators' and co-workers' curricula vitae;
- Copies of all direct correspondence with the IEC/IRB and with the regulatory authority(ies);
- Copies of all relevant correspondence between the investigator and the monitor and between the investigator and the sponsor;
- Copies of investigational device disposition records; and
- Copies of safety information reported during the investigation and submitted by the sponsor.

Trial documents may not be destroyed by site personnel prior to the end of the required retention period, as specified by local regulations. The investigator or the institution must inform the sponsor in due time if the investigator leaves the institution during the retention period. This rule also applies when the institution closes within the retention period.

Upon closure of the trial, the investigator must maintain all trial-site records in a safe and secure location. The investigator is responsible for the integrity, retention, and security of all trial-related records. The investigator must ensure that any reproductions of the original records are legible and provide a true and accurate copy of the original. Accurate, complete, and current records must be stored in a manner to permit easy and timely retrieval for the sponsor or any applicable regulatory authorities.

The sponsor will inform the investigator of the time period for retaining these records to comply with all applicable regulatory requirements, with the minimum retention time being the longest of those times dictated by institutional requirements, local laws or regulations,

or the sponsor's standard procedures. The investigator must notify the sponsor in the event of any changes to archival arrangements due to withdrawal of the investigator's responsibility for keeping trial records to ensure that suitable arrangements for the retention of trial records are made.

14.6 Clinical Trial Report

A clinical trial report containing effectiveness and safety analyses will be generated after all subjects have completed the Day 180 visit. The content of the report will meet China Center of Medical Device Evaluation (CMDE) requirements.

14.7 Publication of Trial Results

The results of this trial and any discoveries related to this trial, regardless of whether they have technical or medical character, are the property of the sponsor.

The CTP, trial data, and information related to the trial or the sponsor's products or research programs are to be kept confidential and may not be disclosed without the consent of the sponsor.

The investigator agrees that the results of this trial may be used for submission to national or international registration and supervising authorities. Upon completion of the trial, publication or disclosure of trial results is to follow the terms contained in the sponsor's publication policy.

The sponsor will ensure the clinical trial is registered, and results are reported in public registries, at minimum in case one or both is required by law and/or other applicable requirements (e.g., on ClinicalTrials.gov if required by U.S. law and/or on Chinese Clinical Trial registry (ChiCTR)). Trial registration may include a list of investigative sites, as applicable.

14.8 Financial Disclosure

Financial aspects of the investigation will be documented in an agreement between the sponsor, the CRO, and each investigator or any other involved party, and must be confirmed in writing before the investigation commences.

14.9 Investigator Compliance

The investigator will conduct the trial in compliance with the CTP, EN ISO 14155, Chinese GCP, the Declaration of Helsinki, and Chinese regulatory authority requirements.

Additional information is reported in Section 14.4.1.

16 APPENDICES

The objective of this statistical analysis plan (SAP) is to specify the statistical analyses with appropriate detail and precision to serve as a guideline for statistical programming and creation of tables, figures, and listings for clinical trial protocol M960101056, version 3.0, dated 08 Jul 2021. CRF, version 2.0, dated 01 Sep 2021.

The Merz standard Table, Figures, and Listings (TFLs) for medical devices, version 2.0 will be applied and adapted to trial specific requirements as laid down in the clinical trial protocol M960101056, version 3.0 and any amendments. These mock TFLs will serve as study-specific output specifications for statistical programming.

Special attention will be paid to planning and performance of quality control measures. Risk scores based on assessments of complexity and impact of errors and quality control measures for statistical programming (including analysis datasets, TFLs, SDTMs, ADaMs as applicable) will be documented in the external NTF named M960101056_NTF_QC_Statistical Programming v1.0 20220307.

2 Clinical Trial Design and Objectives

2.1 Clinical Trial Design

This is a prospective, 180-day, randomized, multicenter, evaluator-blind, controlled trial designed to evaluate the effectiveness and safety of the Ulthera DeepSEE (DS) System improving the appearance of skin laxity of the lower face and submentum. Subjects will be enrolled from participating investigative sites in China. A total of 200 subjects will be randomized 1:1 to either the Treatment Group or Control Group stratified by investigative site.

The Treatment Group will receive a single treatment at Day 1 with the Ulthera DeepSEE System to the midface, lower face, submentum, and upper neck with three DS transducers (DS 10-1.5, DS 7-3.0, and DS 7-4.5) and will be followed for 180 days after treatment.

The Control Group will not receive treatment at Day 1 and will remain untreated until Day 90 (delayed treatment). Following completion of all protocol-mandated assessments at Day 90, the Control Group will receive a single treatment with the Ulthera DeepSEE System to the midface, lower face, submentum and upper neck with three DS transducers (DS 10-1.5, DS 7-3.0, and DS 7-4.5) and will be followed for 90 days after treatment.

For both the Treatment Group and Control Group, the starting energy level (EL) will be EL2 for the DS 10-1.5 transducer, and EL4 for the DS 7-3.0 and DS 7-4.5 transducers.

All subjects will participate in this trial for 180 days and will be evaluated at screening, Day 1, Day 90, and Day 180. Follow-up telephone calls will occur at 3 days and 14 days after treatment. In case of ongoing transient nerve effects 14 days after treatment, trial personnel will conduct

additional follow-up phone calls with the subject every week until 6 weeks after treatment and document the time of resolution.

After a maximum 14-day screening period, the planned trial duration for individual subjects is 180 days (\pm 14 days).

2.2 Randomization

Subjects are randomized balanced (1:1) to one of the following groups:

- Treatment Group: Treatment with the Ulthera DeepSEE System at Day 1; or
- Control Group: Untreated control, with delayed treatment at Day 90.

Randomization will be stratified by investigative site and performed in blocks.

2.3 Blinding

2.4	Unblinding	
group	p assignment.	
For t	he primary effectiveness endpoint only (rs and subjects will not be blinded to trial treatment. proportion of subjects with improvement in lower blinded evaluators will be blinded to trial

2.4.1 Planned Unblinding

Planned unblinding procedures are not necessary in the current tri	al design,	as the	treating
investigator, trial coordinator, sponsor staff, and other trial personnel			
are not blinded to trial group assignments.			

2.5 Trial Objectives

2.5.1 Effectiveness

Demonstrate superiority of treatment with the Ulthera DeepSEE System compared to untreated control for the improvement of skin laxity of the lower face and submental area.

2.5.2 Safety

Demonstrate the safety of treatment with the Ulthera DeepSEE System for the improvement of skin laxity of the lower face and submental area.

[figure not shown]
3 Determination of Sample Size

4	Analysis Sets
Th	e following analysis sets will be defined:
_	The randomized set is defined as all subjects randomized into the trial;
-	The Safety Evaluation Set (SES) is defined as all subjects treated;
_	The Full analysis Set (FAS) is defined as all subjects randomized. Subjects randomized to the Treatment Group must also finish the treatment;
_	The Per Protocol Set (PPS) is the subset of subjects in the FAS who have no major protocol deviations potentially biasing the statistical analysis of the primary endpoint. Final determination of what constitutes major or minor protocol deviations in this sense will be made prior to database close.
5	Endpoints for Analysis
_	
5.1	Effectiveness Endpoints
5.1 5.1	
5.1	
5.1	.1 Primary Effectiveness Endpoint
5.1	.1 Primary Effectiveness Endpoint
5.1	.1 Primary Effectiveness Endpoint oportion of subjects with improvement in lower face and submental skin laxity at Day 90
5.1 Pro	.1 Primary Effectiveness Endpoint oportion of subjects with improvement in lower face and submental skin laxity at Day 90
5.1 Pro 5.1 5.1	.1 Primary Effectiveness Endpoint oportion of subjects with improvement in lower face and submental skin laxity at Day 90
5.1 Pro 5.1 5.1 Dis	.1 Primary Effectiveness Endpoint oportion of subjects with improvement in lower face and submental skin laxity at Day 90 .2 Secondary Effectiveness Endpoints .2.1 Displacement of skin in the submentum at Day 90 splacement of skin (mm) in the submentum at Day 90 .
5.1 Pro 5.1 5.1 Dis	.1 Primary Effectiveness Endpoint oportion of subjects with improvement in lower face and submental skin laxity at Day 90 .2 Secondary Effectiveness Endpoints .2.1 Displacement of skin in the submentum at Day 90 splacement of skin (mm) in the submentum at Day 902.2 Proportion of Subjects with Any Improvement on iGAIS at Day 90
5.11 Pro 5.11 5.11 Dis 5.11 Pro Ae	.1 Primary Effectiveness Endpoint oportion of subjects with improvement in lower face and submental skin laxity at Day 90 .2 Secondary Effectiveness Endpoints .2.1 Displacement of skin in the submentum at Day 90 splacement of skin (mm) in the submentum at Day 90 .

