9.2.1 Inclusion Criteria

To be eligible for trial participation, each subject must meet all of the following criteria at screening (Day -14 to -3; Visit 1 [V1]) and Day 1 (V2):

Healthy male or female aged 35 to 65 years at the time of screening.

Has mild to moderate lower face and/or submental laxity that is amenable to improvement with non-invasive intervention and is not severe enough for surgical intervention.

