9.2.4 Subject Enrollment and Randomization

Subjects are considered to be enrolled once the ICF is signed and dated. Eligible subjects will be randomized during the screening period (Day -14 to -3). Randomization assignment will not be disclosed to the subjects until Visit 2 (Day 1).

Screen failures are defined in Section 9.2.5.

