10.5.2 Selection and Timing of Treatment for Each Subject

Subjects in the Treatment Group will receive a single treatment with the Ulthera DeepSEE System at Day 1 (V2). Subjects in the Control Group will not receive treatment at Day 1 and will remain untreated until Day 90 (V3). Following completion of all protocol-mandated assessments at Day 90 (Section 11.1), the Control Group will receive a single treatment with the Ulthera DeepSEE System.

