13.3 Populations for Analysis

The following analysis sets will be defined:

- The randomized set is defined as all subjects randomized into the trial;
- The Safety Evaluation Set (SES) is defined as all subjects treated;

- The Full analysis Set (FAS) is defined as all subjects randomized

 Subjects randomized to the Treatment Group must also finish the treatment;
- The Per Protocol Set (PPS) is the subset of subjects in the FAS who have no major
 protocol deviations potentially biasing the statistical analysis of the primary endpoint.
 Final determination of what constitutes major or minor protocol deviations in this sense
 will be made prior to database close.

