13.4.1 Effectiveness Analyses

If not otherwise specified, effectiveness analyses will be based on observed cases in the FAS. For the FAS, all subjects will be analyzed as randomized.

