13.4.1.1 Primary Effectiveness Endpoint

The primary effectiveness endpoint is defined in Section 7.2.1.1.

Primary Analysis

The primary analysis of the primary effectiveness endpoint is conducted by using a logistic regression model with fixed effects treatment group and site. Analysis population will be the FAS.

Effectiveness of treatment is confirmed if the p-value of the test is $\leq 5\%$ and the odds ratio is in favor of Treatment (i.e., > 1).

Sensitivity Analyses

The following sensitivity analyses will be conducted to support the primary analysis:

- 1. Observed cases: the same approach as outlined for the primary analysis will be applied to observed cases instead of multiple imputation.
- 2. PPS: the observed cases analysis will be applied to the PPS.

4. Randomized set: the same approach as outlined for the primary analysis will be applied to all subjects in the randomized set

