6.4.4 Multiple Comparisons/Multiplicity

No multiplicity adjustments are required. Only one confirmatory analysis of the primary effectiveness endpoint will be performed.

8 References

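### The primary analysis set drops Treatment Group subjects who do not finish treatment, with no matching exclusion in Control, so the only confirmatory test is not of the groups as randomized.

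*SAP*

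**What the plan says.** SAP section 4 defines the Full Analysis Set (FAS) thus: "The Full analysis Set (FAS) is defined as all subjects randomized. Subjects randomized to the Treatment Group must also finish the treatment". Protocol 13.3 carries the same sentence, "Subjects randomized to the Treatment Group must also finish the treatment", and neither document shows a counterpart for Control. Each defines the randomized set separately, without conditions, so the FAS is meant to be a different set.

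For the primary endpoint, Protocol 13.4.1.1 says "Analysis population will be the FAS". Effectiveness is confirmed if p ≤ 5% and the odds ratio exceeds 1. SAP 6.4.4 adds: "Only one confirmatory analysis of the primary effectiveness endpoint will be performed". The randomized set appears only in sensitivity analysis 4 (Protocol 13.4.1.1, SAP 6.1.1.2).

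On timing, Protocol 9.2.4 places randomization 3 to 14 days before Day 1, and Protocol 9.2.1 requires eligibility at screening and again at Day 1. Under Protocol 10.5.2 the Treatment Group is treated at Day 1 and Control only after its Day 90 assessments.

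**The concern.** Randomization protects a comparison only while the analysed groups are those randomized. Here membership of one group depends on an event after assignment that the other group cannot experience before the endpoint.

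Two kinds of Treatment Group subject are lost. One is the subject whose session is stopped part-way, which Protocol 6.3 and 9.2.6.1 foresee. The other is the subject who withdraws or fails eligibility between randomization and Day 1 and is never treated. On the visible text, the same kind of Control subject stays in the FAS.

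Either kind may plausibly improve less than a subject who received the full treatment, and removing them would then raise the Treatment response rate. The claim at stake is superiority over untreated control, and it is decided by this one test. The visible text also does not say what counts as finishing. Protocol 10.5.1.3 plans 820 treatment lines with up to 10% more at discretion, and the treating investigator is not blinded (Protocol 10.4.1).

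**Working it through.** **Who is in the FAS, on the visible text**

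| Event before Day 90 | Treatment Group | Control Group |
|---|---|---|
| Withdraws or fails eligibility between randomization and Day 1 | out | in |
| Session stopped part-way | out | cannot occur |
| Session finished | in | cannot occur |

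Two provisions might seem to repair this. The statement "For the FAS, all subjects will be analyzed as randomized" settles which arm a subject counts in, not whether the subject is in the set. Multiple imputation, implied by sensitivity analysis 1, fills missing Day 90 values for members of the set and does not bring back those excluded.

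**Inputs.** From the documents: 200 subjects randomized 1:1, so about 100 per arm; two-sided 5% test; success requires p ≤ 5% and OR > 1. The visible text gives no completion or response rates, and the sample-size reasoning is not public, so there is no plan figure to reproduce. All rates below are assumptions.

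**Bias in the response rate.** The FAS rate is pF. The all-randomized rate is (1 − q)·pF + q·pN. The difference is q·(pF − pN).

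**Effect on the odds ratio.** Assume finishers 70% and Control 20%. The FAS odds ratio is (0.70/0.30)/(0.20/0.80) = 9.33. At q = 10% and pN = 20%, the all-randomized rate is 0.9 × 0.70 + 0.1 × 0.20 = 0.65. The odds ratio is then (0.65/0.35)/0.25 = 7.43, and 9.33/7.43 = 1.26. Overstatement of the odds ratio:

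| q | pN = 70% | pN = 45% | pN = 20% | Largest overstatement of Treatment rate |
|---|---|---|---|---|
| 2% | 0% | 2% | 5% | 1.0 point |
| 5% | 0% | 6% | 12% | 2.5 points |
| 10% | 0% | 12% | 26% | 5.0 points |
| 15% | 0% | 19% | 40% | 7.5 points |

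**Effect on a false positive.** Assume a true rate of 30% in both randomized arms and 100 per arm. Finishers then respond at pF = (0.30 − q·pN)/(1 − q). For q = 10% and pN = 0, pF = 0.30/0.90 = 0.333, and the FAS odds ratio is (0.333/0.667)/(0.30/0.70) = 1.17 when the truth is 1. The test simulated is an unadjusted two-proportion z-test, standing in for the planned logistic regression with site. The number of non-finishers is Binomial(100, q), removed from Treatment only; success is z ≥ 1.96; there were 2,000,000 replicates. Chance of wrongly confirming effectiveness:

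| q | pN = 30% (unrelated to outcome) | pN = 15% (half the overall rate) | pN = 0% |
|---|---|---|---|
| 2% | 2.5% | 2.8% | 3.1% |
| 5% | 2.5% | 3.3% | 4.3% |
| 10% | 2.5% | 4.4% | 7.1% |
| 15% | 2.5% | 5.9% | 11.7% |

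A normal-approximation calculation agrees to within about 0.1 percentage point.

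**The case against.** The best case for the plan has five parts.

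- **The difference will be seen.** Sensitivity analysis 4 repeats the primary approach in all randomized subjects. This stands as a means of detection. It does not decide success, so if the two analyses disagree, the FAS result still rules.
- **The worst scenarios are extreme.** If the device does nothing, failing to finish cannot itself lower response; the gap would need prognostic selection. With non-finishers at 25% or 20% against 30% overall, the false-positive chance is only about 2.8% or 3.1% at q = 5%, and 3.0% or 3.7% at q = 10%. Treatment is one session, energy can be reduced, and sites are told to try to complete it (Protocol 9.2.6.1), so a high q is not supported. This bears on size and stands. In the 70% versus 20% example, power is effectively 100% either way, so only the estimate is affected.
- **Assignment is withheld from subjects until Day 1** (Protocol 9.2.4), so an earlier withdrawal is not a reaction to it. That is true, but the resulting exclusion is still one-sided, and trial staff know the assignment (Protocol 10.4.2).
- **Protocol 13.3 has a gap just before the completion sentence**, so a condition covering both arms may be withheld. This weakens certainty about Control subjects lost before Day 1. It does not remove the visible Treatment-only condition.
- **Using all randomized subjects is not a full cure** if those without Day 90 data are imputed as though they had finished. This stands, and the fix has to address it.

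**Conclusion.** The concern holds. The FAS applies a post-randomization exclusion to one arm, and it is the population of the only confirmatory test. The direction and size of the bias cannot be determined from the documents. It is zero if non-finishers respond like finishers and favours the device if they improve less. Under the stated assumptions the false-positive chance ranges from 2.5% to 4.3% at 5% non-completion and from 2.5% to 7.1% at 10%. The upper ends require that no non-finisher improves. The case for changing the plan rests on the visible rule and not on any one of these figures: the sole test should not depend on an unknown that one sentence introduces.

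**What to change.** Delete the completion sentence from the FAS definition in Protocol 13.3 and SAP section 4, so that the primary analysis covers all randomized subjects as randomized. If a finishers-only analysis is wanted, put the condition in the Per Protocol Set (PPS) or a separately named supportive set, with an objective definition of finishing.

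Reconcile the follow-up text. Protocol 6.3 and 9.2.6.1 describe follow-up after stopped treatment in safety terms, while 9.2.6.2 and 11.1.1 call for every subject to be followed with all scheduled assessments. The Day 90 effectiveness assessment should be sought for every randomized subject whether or not treatment was finished. Confirm also that the imputation model does not treat never-treated or partly treated subjects without Day 90 data as finishers.

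The cost is mainly wording, since both populations are already planned. The FAS is the default for all effectiveness analyses and the PPS is a subset of it, so the secondary analyses and PPS membership change too. The estimate may be less favourable and some power may be lost. For example, with assumed rates of 40% in finishers and 20% in Control, q = 10% and 100 per arm, power is 86% in the current FAS (90 versus 100). In all randomized subjects the Treatment rate becomes 40%, 39% or 38% if non-finishers respond at 40%, 30% or 20%, and power is 88%, 85% or 81%.
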